#### 7.1.2 Exclusion criteria

- Men who are on remand.
- Men who are convicted sex offenders.
- Men who are due for release or transfer to another prison during the 9-week HDHK-P program.
- Men who themselves (or whose families) have a history of conflict with other men/families on the program.
- Men (or their family members) who cannot read/speak sufficient English to give informed consent.

#### 7.2 Sampling

The Phase 1 feasibility study aims to recruit ~8-10 imprisoned men each with 1-2 children aged 8-11 years to two sequential deliveries of HDHK-P: one delivery in HMP Perth followed by one delivery in HMP Barlinnie. Total N: men 16-20; children ~16-32.

The Phase 2 pilot evaluation aims to recruit 8-10 imprisoned men each with 1-2 children aged 8-11 years to four deliveries of HDHK-P at HMP Perth and HMP Barlinnie. The program will be delivered sequentially twice (deliveries A and B) in each prison. Total N: men 32-40; children ~32-64.

Phase 2 will also include interviews with 4-8 HDHK-P facilitators, ~6-8 prison/Scottish Prison Service administrative/managerial staff, and ~16 of the adults accompanying children to HDHK-P sessions in the prison.

#### 7.2.1 Size of sample

The target sample sizes have been guided by discussions with PEIs and family contact officers, who have suggested maximum group sizes of 8-10 fathers and 8-16 children would be practical and feasible for each HDHK-P delivery.

## 7.2.2 Sampling technique

Convenience sampling guided by advice from the PEIs and family contact officers will be used for both phases.

## 7.3 Recruitment and sample identification

The recruitment strategies and procedures finalised during the WP1 stakeholder consultations will be used to recruit the imprisoned fathers and their children to all HDHK-P deliveries. It is anticipated that family contact officers will liaise with the PEIs to identify suitable men and families to approach to ask whether they would like to take part in HDHK-P, based on their knowledge of potential participants. Established prison protocols will be used to minimise and manage any risks (for example, checking there are no existing or recent conflicts between the participating men and/or their families). It is expected that approaches to all men and their families will be made directly by the PEIs and family contact officers. All potential participants (men, families and children) will be asked to opt in to the study

## 7.3.1 Consent

Informed consent will be obtained from all fathers and accompanying adults before their participation in the study. Informed assent will be obtained from all participating children before the start of their involvement in the study. During recruitment, the PEIs and family contact officers will provide potential participants with the appropriate study information sheet, which will outline the purpose of the research, their role in it, and will explain that participation is entirely voluntary, confidential and can be stopped at any time. The PEIs and family contact officers will be trained to answer questions that people might have (as identified during the WP1 stakeholder consultation), and a member of the research team will be available to support them with additional information, as required.

The informed consent/assent procedure for fathers, their children and accompanying adults will be conducted by a trained member of the research team prior to participants' involvement in the study. The researcher will explain the aims of the study, and the benefits and potential risks to ensure that participants fully understand what taking part will mean for them, and will give them an opportunity to ask further questions about any aspect of the study. The researcher will also ensure they are satisfied that participants fully understand the nature and purpose of study, their involvement in it and that it is their choice to take part before they sign the consent/assent forms. The precise location of the informed consent/assent procedures will be confirmed during the WP1 stakeholder consultations.

HDHK-P facilitators and prison management/administrative staff will be provided with a study information sheet by a member of the research team and will be given an opportunity to ask questions and/or discuss any aspect of the research. The researcher will then take informed consent (as described above) prior to the facilitator's/staff member's involvement in the study (i.e., HDHK-P session delivery and/or interviews).

All study documentation will be carefully prepared to ensure it is appropriate for each potential participant group (including adults with low literacy levels and primary school aged children). It will be approved by university and prison research ethics committees.

## 8 ETHICAL AND REGULATORY CONSIDERATIONS

The research is designed to optimise and pilot a prison-based intervention (HDHK-P) that will be delivered to imprisoned men and their children. People in custody and their families are amongst the most marginalised members of society, often experiencing socioeconomic disadvantage before imprisonment, which deepens even further following incarceration (16).

The research process is guided by the principles of informed consent, participatory collaboration, and of doing no harm to participants. Pertinent ethical considerations include ensuring that participation in HDHK-P is experienced as an enhanced form of family visiting at all times and does not detract from

existing family contacts for participating children and/or their siblings, and that HDHK-P deliveries are attuned both to the needs of imprisoned fathers and their children, and facilitate family ties characterised by the principles of reciprocity (62). In addition, the dark logic model developed in WP1 will be used to monitor potential harms throughout the study, and a safeguarding protocol will be developed during WP1, which will set out actions should any harm to those involved in the study be detected. Finally, it is important that there are attempts to sustain the father-child engagement promoted by HDHK-P following completion of the program. Stakeholder and family engagement conducted as part of WP1 will explore these issues, including whether/how the Scottish Prison Service or other agencies can deliver follow-on activities to the program. Potential follow-on activities for consideration include: fathers who participated in the program continuing to meet every 6-8 weeks; and initiatives to support ongoing father-child physical activity (e.g., Families Outside has worked with the Dennis Law Legacy Trust to deliver its Streetsport program to parents and children, and a Children in Need funded initiative has run sporting activities at some family visits at HMP Grampian).

Many prison-based interventions, including HDHK-P, seek to break cycles that make inequalities in health and other outcomes so persistent, as well as trying to address current inequalities (16). The children of imprisoned parents have been identified as key in current Scottish Government efforts to tackle child poverty, and the inequalities surrounding this (63). Overall, therefore, we believe that the benefits to the imprisoned men, their children, other family members, communities and society as a whole outweigh any possible discomfort or inconvenience to participants during the course of the study.

#### 8.1 Assessment and management of risk

A number of potential risks have been identified as follows:

Discussion of sensitive topics: Talking about parenting and father-child relationships in a group context may be distressing for some fathers, as it may lead them to reflect negatively on their own parenting experiences and skills, and generate feelings of shame. The PEI facilitators, who are skilled at dealing with men in custody and the personal problems they present, will receive further training from the research team in how to deal with any relationship issues that may be revealed during HDHK-P (e.g., making time to talk to the father individually during/after a session). All issues raised will be reported to the co-Cls and, if appropriate, referred to the relevant support service within the prison. The precise safeguarding procedures to be followed will be developed during the WP1.

In addition, we will explore the experiences of taking part in HDHK-P in qualitative interviews/discussions with fathers, children, accompanying adults and PEI facilitators. Participants in these interviews/discussions will be reminded that they do not have to answer any question they do not want to, and that they can terminate the interview/leave the discussion at any point. Researchers will also be trained to be sensitive to the impacts of the interviews/discussions; they will monitor participants for signs of distress throughout and pause the interview/discussion if they feel that a participant needs a break.

If a participant discloses any intent to harm themselves or others at any time during participation in the study (HDHK-P sessions, interviews/discussions, measurements) the co-CIs and relevant prison authorities will be informed. All participants will be made aware of this during the informed consent process prior to their participation in the study.

Participants being transferred to another prison during the program: There is a significant amount of movement of men in custody from prison to prison within the Scottish Estate. We have assurance, however, that any men taking part in an intervention like HDHK-P are now routinely ring-fenced for the duration of the intervention and will not be transferred during this time, unless there are exceptional circumstances.

Poor quality relationships or conflict between participants/accompanying adults, or vice versa, during sessions: Family contact officers and PEIs will consider any known interpersonal conflicts between men and families when they select potential participants to approach for each delivery of HDHK-P, as they do routinely with all interventions to minimise these risks. The PEIs, family contact officers and their colleagues have detailed knowledge of the men and their families.

Low response rates at 6- and 9-month follow-up measures: Low response rates are more likely for men who have transferred to another prison (movement is only protected during the period of active delivery of the intervention) or who have been released, than for those remaining in the same prison. However, we believe that the strong connections developed with the men and their families by the researchers and the PEIs during HDHK-P sessions will facilitate follow-up even where men have been transferred or released. Efforts will also be made to maintain good communication with the families, as appropriate, following program completion (precisely how this will be done will be explored in the WP1 stakeholder consultations). In addition, we will stress to families the important role that they have in determining whether HDHK-P will be continued for other families in future, and hence the value of their participation. Finally, we will draw on the expertise of project team members in conducting prison research over many years to develop the procedures for follow-up in the community.

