WP2 will pilot two deliveries (A and B) of the optimised HDHK-P in the same two prisons (four deliveries in total) and will assess research procedures for a future full-scale evaluation. The research team will observe program sessions and conduct: in-depth interviews with the PEI facilitators, the participating fathers and the adults accompanying the children to program sessions; and group discussions with the participating children. Baseline and follow-up measures (at 9 weeks and 6 months for deliveries A and B, and at 9 months for delivery A) will collect data on fathers' mental health and wellbeing (likely primary outcome in a future full-scale evaluation), and a selection of the following potential secondary outcomes in a future full-scale evaluation (to be finalised in WP1): father and child self-esteem, father discretionary food/drinks prison canteen purchases, father and child self-reported dietary intake, father and child physical activity, father and child weight, child screen time, quality of the father-child relationship from both perspectives, and child socio-emotional health and self-worth.

WP3 will involve a wider prison consultation with regard to future full-scale evaluation and rollout. An optimized HDHK-P program will be a key output of the study. Progression to a full-scale evaluation will make use of a red-green-amber system designed to assess: positivity about the program among stakeholders; and aspects of delivery and sustainability that are pertinent to such an evaluation being possible. The possibility of embedding the program in the Scottish's Prison Service's Family Strategy will also be explored.

Study Title	Healthy Dads Healthy Kids in Prisons: a feasibility study and pilot for an intervention to improve father-child relationships
Internal ref. no. (or short title)	HDHK-P Feasibility and Pilot Study
Study Design	A mixed-method two phase feasibility study and before-and- after pilot evaluation
Study Participants	Incarcerated fathers and their children aged 8-11 years in two Scottish Prisons (HMP Perth and HMP Barlinnie)
Planned Size of Sample (if applicable)	Phase 1 Feasibility study: 16-20 fathers each with 1-2 children
	Phase 2 Pilot study: 32-40 fathers and 32-64 children (and HDHK-P facilitators (N=2-6), prison administrative/managerial staff (N=6-8) and adults accompanying children to attend intervention sessions at the prisons (N~16))
Follow up duration (if applicable)	Phase 1 Feasibility study N/A

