health or wellbeing (such as the Patient Health Questionnaire (50) or General Health Questionnaire (51)). Secondary outcomes may include: fathers' and children's self-esteem (Rosenberg's Self-Esteem Scale (52)), fathers' discretionary food and drink purchases from the prison canteen (via routine prison data, which project team members have experience of analysing in relation to smoke-free policy implementation (42)); fathers' and children's self-reported dietary intake (using Scottish Health Survey measures (53) - sweets/chocolate; crisps/snacks; sugar-sweetened beverages; chips; processed meat; ice-cream), children's socio-emotional health (Strengths and Difficulties Questionnaire (20), Children's Society Good Childhood Index (54)), fathers' and children's physical activity (self-reported using pedometer step counts or objectively measured), fathers' and children's weight; children's screen time, quality of father-child relationships from the perspectives of both the father and child (Parent-Child Relationship Questionnaire) (55), and children's self-worth (the Self-Perception Profile for Children) (56). Not all of these outcomes will be collected: the WP1 key stakeholder consultations will inform final decisions about how much and what kind of outcome data it is acceptable to collect (and how). In addition, collecting health economics resource use data from prisoners and their children is likely to be problematic. Consultations with the Scottish Prison Service in WP1 will therefore be used to establish what economic information they would need for decision-making on whether to embed HDHK-P in the prison service, and test the feasibility and acceptability of collecting these data in WP2.

The extent to which, and how, follow-up measurements can be obtained from men who have been released from prison (and their children) during the study will also be explored. This is likely to involve building further on the relationships built up with men and their families during intervention delivery.

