Data analysis: Qualitative data will be transcribed and analysed thematically using a framework approach (57) to explore: barriers and facilitators to program implementation and delivery; participant engagement, involvement and retention; and views on/the experience of/reported benefits and disadvantages of participation in the intervention. Data from the session observations, and the interviews/group discussions with the father and child participants, the accompanying adults, the PEI intervention facilitators and other prison staff will be triangulated to allow evaluation of HDHK-P from multiple perspectives. For outcome measures, the completion rates and change in these measures will be assessed. The economic analysis will assess the feasibility of resource use and outcome data collection and valuation. For resource data, the cost of the HDHK-P intervention will be explored, and the key cost drivers identified. A descriptive log of methodological issues will be kept and analysed.

5.2.2 WP3: wider prison consultation with regard to full scale evaluation and rollout (Objective 3, RQ 5) Interviews with key staff (PEIs, family contact officers, governors and others) from all Scottish prisons (except those that house only young offenders or women) (N=13 prisons) will be arranged to explore views on any barriers to delivery in individual prisons (e.g., geography, meaning it would be difficult for families to attend deliveries of the intervention; open prison, meaning the enhanced contact is not seen as necessary by potential participants), willingness to participate in a future full-scale evaluation (e.g., a randomised controlled trial), and the potential for future scaling-up of HDHK-P across Scottish prisons.

Progression criteria: The criteria for progressing to a full-scale evaluation will make use of a red-ambergreen system (58, 59) applied to the data collected in WP2, with respect to:

1) program content: green – over 75%; amber – 55-75%; red – below 55%, of fathers, accompanying adults and children who participate in the interviews/group discussions are largely positive about the intervention.

2) delivery and sustainability:

a. green – 8-10; amber – 6-7; red – fewer than 6 men and their children, on average, are recruited to each delivery;

b. green – over 70%; amber – 55-70%; red – below 55% of men screened are eligible for the program;

HDHK-P Feasibility and Pilot Study

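### The follow-up retention message ties families' participation to the program's continuation, which may tilt follow-up self-reports favourably in a pilot with no comparator

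*Protocol*

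**What the plan says.** Section 8.1 of the Protocol lists low response at the 6- and 9-month measures as a risk. Among the remedies it states that "we will stress to families the important role that they have in determining whether HDHK-P will be continued for other families in future", and it closes the sentence with the purpose: "and hence the value of their participation". The same paragraph relies on the ties that researchers and PEIs form with men and families during the sessions, and it leaves the manner of keeping in touch with families to WP1.

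The Study Summary gives the design as "A mixed-method two phase feasibility study and before-and- after pilot evaluation". Section 5.2.1 (Method 4) lists the candidate outcomes. The likely primary outcome is a questionnaire on fathers' mental health or wellbeing. The secondary candidates include "fathers' and children's self-reported dietary intake" and "quality of father-child relationships from the perspectives of both the father and child", together with self-esteem, socio-emotional health and self-worth scales. Three candidates need not rest on self-report: canteen purchases from routine prison data, weight, and physical activity if it is measured objectively. The list is provisional until WP1. The data analysis paragraph says that completion rates and change in the measures will be assessed, and Method 4 is assigned to RQs 3 and 5.

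Progression criterion 1 (section 5.2.2) is the share of fathers, accompanying adults and children "who participate in the interviews/group discussions are largely positive about the intervention". Appendix 2 places the interviews and group discussions post-program.

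**The concern.** The reason given to families for staying in the study is the future of the program. A family that values the extra contact could reasonably conclude that good reports help to keep it going. The message belongs to the follow-up phase, so it can alter follow-up answers while baseline answers stay as they were. Without a comparator, such a shift goes straight into the before-and-after change.

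At stake is the reading of RQ3, which asks about the program's potential to deliver its target outcomes. A reporting shift would make that potential look better than it is and could not be removed once the data are in. The consent and interview safeguards (sections 7.3.1 and 8.1) cover voluntary participation, skipping questions and stopping. Nowhere does the Protocol say that families will be told critical answers are as useful as favourable ones.

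**Working it through.** The plan states no figure on this point, so there is none to reproduce. The check is of the text, followed by two illustrations whose key inputs are assumptions.

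**1. Who hears the message, and when.** Section 8.1 speaks of the men and their families as distinct groups and addresses this message to families. It concerns the 6- and 9-month measures. It therefore bears first on child and carer reports at those times, and on fathers' reports only if it is passed on to them. Baseline precedes it.

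**2. Can the design reveal a shift?** Let the true mean change be D and the reporting shift at follow-up be b. The observed mean change estimates D + b. A comparator given the same message would allow b to cancel in the difference between groups. This pilot has no comparator, so D and b cannot be separated. Measures not based on self-report would escape b, but they are few and not yet confirmed.

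**3. Illustration for a change score.** Assumptions: a shift of 0.2 SD, a correlation of 0.5 between baseline and follow-up, equal SDs and independent respondents. The lower planned number is 32, for fathers and for children alike.

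- SE of mean change = SD × √(2(1 − 0.5)/n).
- n = 32: SE = 0.177 SD, and 0.2/0.177 = 1.13 standard errors.
- n = 22 (about 70% of 32 retained): SE = 0.213 SD, and 0.2/0.213 = 0.94 standard errors.

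A shift of that size would be as large as the sampling error and would look like modest benefit. The 0.2 is not taken from the documents.

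**4. Illustration for criterion 1, only if the message comes before or around the interviews.** Section 5.2.1 gives about 8 fathers and about 4 accompanying adults per delivery, so 32 and 16 over four deliveries. It gives about 8 children without saying whether this is per delivery or in total, so 8 to 32. The total is 56 to 80, of whom 24 to 48 are family members. Green (over 75%) needs at least 43 of 56 or 61 of 80. The true positive share is assumed to be 70% (amber), and the chance of green is an exact binomial tail. Where only families shift, it is the tail of the sum of two binomials: 32 fathers at 0.70, and the family members at 0.70 plus the shift.

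| Shift in share positive | n = 56, all shift | n = 56, families only | n = 80, all shift | n = 80, families only |
|---|---|---|---|---|
| none | 0.17 | 0.17 | 0.14 | 0.14 |
| +5 points | 0.45 | 0.27 | 0.46 | 0.30 |
| +10 points | 0.78 | 0.40 | 0.84 | 0.54 |

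The families-only columns are nearer to what section 8.1 describes. For an overall shift of 5 points, the family members alone would have to shift by 5 × 56/24 = 11.7 points at n = 56, or 5 × 80/48 = 8.3 points at n = 80.

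**The case against.** The strongest reply is that the sentence asks families to take part, not to answer favourably. Its closing clause gives participation as the purpose, and it stands under a response-rate risk. That is right, and it rules out reading the text as soliciting good reports. It does not remove the incentive that the argument creates.

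The message is also broadly accurate. Stated positivity (criterion 1), family consent or assent (2d) and men's 6-month retention (2e) all feed the progression decision, and any red result stops progression. Telling families that nothing they do bears on the program's future would therefore be untrue. This stands, and it limits what the replacement may say.

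A reader might infer that the message biases a progression criterion. The documents do not support that as it stands. No criterion uses change scores. Criterion 1 rests on post-program interviews, while the message concerns later follow-up, and its timing is not fixed. Nor do the documents say that change scores will drive the choice of outcomes for the full trial, or that the staff who observed sessions will administer the follow-up questionnaires.

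There are partial safeguards. The interviews ask about disadvantages and suggested changes and include fathers who do not complete the program, sources are triangulated with session observations, and a dark logic model looks for harms. These help the qualitative findings more than the questionnaire change scores.

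**Conclusion.** The point holds in a limited form. A follow-up retention message linked to continuation of the program, in an uncontrolled before-and-after pilot with mostly questionnaire outcomes, may push child and carer self-reports in the favourable direction at follow-up, and fathers' reports too if it reaches them. That push could not be separated from change after the program when RQ3 is read.

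The likely direction is an inference from the wording and the design. The size is unknown and cannot be derived from the documents; the 0.2 SD, the 0.5 correlation, the 70% share and the 5- and 10-point shifts are all assumptions. An effect on criterion 1 is conditional on timing. Since this is a pilot without a formal test of effectiveness, the harm is confined to how the changes are interpreted. This is a cheap improvement, not an error or a contradiction in the plan.

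**What to change.** In section 8.1 and in the contact script to be settled in WP1, replace the appeal to continuation with three statements:

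- taking part in follow-up is valuable whatever the family's experience of the program has been;
- frank answers, good or bad, are equally useful;
- individual answers will not affect that family's own visits or treatment.

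Do not state that the results have no bearing on the program's future, because the progression criteria make that untrue. Where feasible, have the follow-up questionnaires completed privately by the respondent on the tablets already planned in section 8.6.

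The cost is one sentence and the script, and the change can be made before pilot data exist. The downside is possibly slightly lower motivation to attend follow-up; the general appeal to take part remains.
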